2. METHODS

2.1. PK Analysis

2.1.1. PK Population

The PK population includes all patients who received at least one infusion of IMGN853 and have evaluable PK data. All patients who received IMGN853 and had samples collected with no major deviations related to administration of study drug will be included in the PK population.

2.1.2. Data Handling

Analysis-ready PK datasets will be constructed from audited and locked clinical databases. The data and dosing information will be formatted for PK analysis and saved in ASCII format using R software, Version 3 or higher ([R Core Team 2015](#)). All data manipulation programs will be documented and archived to maintain an audit trail, and will be subject to quality review.

Individual data for all PK subjects will be tabulated by patient and summarized by time point, dose level, and cycle, unless stated otherwise.

2.1.3. Data Presentation

The number of significant digits displayed for the individual values of plasma concentrations will be based on the number of significant figures in the source data. The following descriptive statistics will be reported for each nominal sampling point and PK parameter: number of observations (N), mean, geometric mean, standard deviation (SD), minimum (min), median, maximum (max), coefficient of variation (CV) (CV = SD/mean, expressed as %), and 95% confidence interval (CI) of the mean. The number of significant digits given for the descriptive statistics will generally exceed that of the source data by one. The min and max will have the same number of significant digits as the source data, and CV% will be quoted to one decimal place. If the mean, geometric mean, or median are below the lower limit of quantification (LLOQ), these statistics will be reported as below the quantifiable limit (BQL) and ignored in the calculation of geometric mean. The SD, CV%, and 95% CI will not be calculated (NC) when less than three individual values are available. The other descriptive statistics will be determined when at least one value is reported. Descriptive statistics will be calculated using R software.

2.1.4. Analysis of PK Data

All the PK analyses will be performed using the PK population, and will be conducted similarly for the Schedule A, Schedule B, and Dose Expansion cohorts. Initially, individual and mean concentrations for IMGN853, total antibody (TAb), DM4, and s-methyl-DM4 will be plotted vs. time by dose level for data collected in Cycles 1 and 3. The PK parameters listed in [Table 1](#) will be calculated from these data via standard non-compartmental methods ([Gabrielsso 2016](#)), and the results will be tabulated and summarized by Cycle and dose level. The PK data will be evaluated for dose proportionality and accumulation of each analyte will be assessed.

The observed concentrations for end of infusion in Cycles 2, 4, 5, and 6, as well as end of treatment and follow-up will be summarized and tabulated, but will not be analyzed further.

Table 1: PK Parameters to be Calculated from Data Collected in Cycles 1 and 3

PK Parameter	Definition
C_{\max}	Maximum plasma concentration observed
C_{last}	Final observed plasma concentration above LLOQ
AUC_{∞}	Area under the plasma concentration versus time curve extrapolated to infinite time
AUC_{last}	Areas under the plasma concentration versus time curve from time of dose until T_{last}
T_{\max}	Observed first time to reach C_{\max}
T_{last}	Time corresponding to the last concentration above the limit of quantification
$t_{1/2}$	Terminal half-life
CL	Clearance, i.e. volume of plasma that is completely cleared of the drug per unit time
V_{ss}	Volume of distribution at steady-state

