1.10.2. Rationale to Explore a Modified Weekly Dosing Schedule

As described in Section 1.10.1 a significant correlation between high C_{max} values ($\geq \sim 150 \mu g/ml$) and incidence of ocular toxicity was observed across the 5 and 7 mg/kg dose levels when IMGN853 was

ImmunoGen, Inc. Confidential Page 45 of 138

administered on day 1 of a 21-day cycle dosed by total body weight. Alternate dosing schedules were explored via simulation to identify the dose levels that would achieve maximal exposure with limited accumulation and a C_{max} below 150 μ g/ml in order to minimize ocular toxicity risk.

A population PK model based on rich and sparse (peak and trough) concentration-time profiles of IMGN853 following Q3W dosing (escalating dose) was developed. Plasma concentrations of IMGN853 were best modeled by a 3-compartment model and this model was used to simulate steady-state exposure to IMGN853 for various dosing schedules, including weekly (QW), every 2 weeks (Q2W), and weekly for 3 weeks in a 4 week cycle (modified weekly schedule).

The modified weekly dosing regimen had minimal accumulation between cycles (accumulation index of 1.06), while the QW dosing regimen resulted in the highest accumulation (accumulation index of 1.97). Comparing doses that gave equivalent C_{max} levels, the modified weekly schedule allowed overall exposure increases of almost ~2-fold while limiting C_{max} to levels below that observed with ocular toxicity (Table 2).

				8 8	
Schedule	Dose	C_{max}	C_{min}	C_{avg}	AUC _{12W}
	(mg/kg)	(μg/ml)	(μg/ml)	(μg/ml)	(h*mg/ml)
Q3W	4.2	112	7.8	30	61
Q2W	4.1	119	18	44	89
QWx3 in 4W	3.3	119	20	52	107

Table 2: PK Simulation to Evaluate Fractionated Dosing Regimens

The population PK model was also used to simulate a hypothetical population of 500 patients via Monte Carlo resampling. Descriptive statistics were derived in order to determine a dosing regimen with the percentage of subjects with $C_{max} < 150 \, \mu g/ml$ to optimize the safety profile of IMGN853. Using total body weight dosing, for the Q3W regimen, dose levels of 2.0, 3.3, and 3.8 mg/kg resulted in 99%, 95% and 90% of the population with a $C_{max} < ^{\sim}150 \, \mu g/ml$, respectively. For the modified weekly regimen, dose levels of 1.5, 2.0 and 2.5 mg/kg per dose (or 4.5, 6, and 7.5 mg/kg per cycle) resulted in 99%, 95% and 90% of the population with a $C_{max} < 150 \, \mu g/ml$, respectively.

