6.2.2. Schedule B

Blood samples for PK measurements will be taken in at the following time points:

Cycle 1 & 3:

Day 1 – predose, and following completion of infusion at the following timepoints: 0-10 minutes, and 2 and 4 hours (± 10 minutes)

Day 2 – 24 hours after completion of infusion (± 2 hours)

Day 8 – predose and within 10 minutes of completion of the infusion

Day 15 – predose, and following completion of infusion at the following timepoints: 0-10 minutes, and 2 and 4 hours (± 10 minutes)

Day 16 – 24 hours after completion of infusion (± 2 hours)

Day 22 – a single blood sample will be drawn for PK (\pm 24 hours)

Additionally, a single pre-dose sample will be collected before the IMGN853 infusion and following completion of the infusion in Cycles 2, 4, 5 and 6. A single blood sample for analysis

ImmunoGen, Inc. Confidential Page 80 of 138

of HAHA and HADA will be taken on Day 1 of Cycles 2, 4, and 5 and at the End of Treatment and Follow-up visits.

The sample for HAHA and HADA analysis will be taken from the PK tube; no additional blood draw is necessary.

Details of sample preparation and shipping are provided in the Laboratory Manual.

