1.3.2. Schedule B

Blood samples for PK measurements were taken in at the following time points:

Cycles 1 and 3:

Day 1 – Pre-dose, immediately following completion of infusion (+10 minutes), 2 hours (± 10 minutes) following the completion of infusion, and 4 hours (± 10 minutes) following the completion of infusion

Day 2 – 24 hours after completion of infusion (± 2 hours)

Day 8 – Pre-dose and immediately following completion of infusion (+10 minutes)

Day 15 – Pre-dose, immediately following completion of infusion (+10 minutes), 2 hours (± 10 minutes) following the completion of infusion, and 4 hours (± 10 minutes) following the completion of infusion

Day 16 – 24 hours after completion of infusion (± 2 hours)

Day 22 – a single blood sample for PK (± 24 hours)

Cycles 2 and 4 through 6:

Day 1 – Pre-dose and immediately following completion of infusion (+10 minutes)

End of Treatment**28 Day Follow Up****1.3.3. Additional Samples**

Per study protocol, any patient who experienced a Grade 2 or greater infusion reaction during the administration of IMGN853 had blood drawn within 3 hours of the onset of the reaction and one week later for determination of drug concentration and antibodies to IMGN853.

PK samples were also obtained, as feasible, any time during the treatment period for assessment of study drug related SAEs if deemed appropriate by the Investigator and Sponsor.

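### Schedule B half-life rests on two samples beyond 4 h, at 24 h and about 168 h, so it is poorly determined and probably short, while the pre-dose sample at about 336 h has no assigned role

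*SAP*

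**What the plan says.** Protocol 2.4 and SAP 2.2.2 list terminal half-life, clearance and Vss among the secondary endpoints. PK plan 2.1.4 computes them, with AUC-infinity, by standard non-compartmental methods from data collected in Cycles 1 and 3, and states that the analyses "will be conducted similarly for the Schedule A, Schedule B, and Dose Expansion cohorts". It gives no rule for how many points, what time span or what quality of fit a terminal slope needs.

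Sampling in those cycles differs between schedules (PK plan 1.3.1 and 1.3.2):

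- **Schedule A:** up to 4 h or later on Day 1, then 24 h, 48 h, Day 4 or 5, Day 8 and Day 15.
- **Schedule B, Day 1 dose:** end of infusion, 2 h and 4 h, then "Day 2 – 24 hours after completion of infusion (± 2 hours"), then the sample before the next dose, "Day 8 – Pre-dose and immediately following completion of infusion (+10 minutes").
- **Schedule B, Day 15 dose:** the same early times, then "Day 16 – 24 hours after completion of infusion (± 2 hours") and "Day 22 – a single blood sample for PK (± 24 hours").

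Protocol 6.2.2 adds that "a single pre-dose sample will be collected before the IMGN853 infusion and following completion of the infusion in Cycles 2, 4, 5 and 6". Section 2.1.4 sends the end-of-infusion samples of those cycles, and the end-of-treatment and follow-up samples, to tabulation only. It does not mention the pre-dose samples.

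**The concern.** Protocol 1.10 gives a half-life of about 5 days at 2.0 mg/kg and above, and Protocol 1.10.2 says concentrations were "best modeled by a 3-compartment model". With several phases of decline, a slope through 24 h and 168 h describes the terminal phase only if distribution has finished by 24 h. If it has not, or if the 4 h sample is added to reach three points, the slope is too steep and the half-life too short. Schedule A has samples out to Day 15 and suffers less. The same kinetics could then show a shorter half-life on Schedule B purely because of when blood was drawn. AUC-infinity would be too low and CL too high. A later sample that would help is already in the freezer, but the restriction to Cycle 1 and 3 data gives it no place.

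**Working it through.** **1. Span.** (168 − 24) / 120 h = 1.2 half-lives at 5 days. The ±24 h window on Day 22 makes this 1.0 to 1.4. The next cycle's Day 1 falls 14 days after Day 15, at 336 h: (336 − 24) / 120 = 2.6 half-lives. A 3-day delay, which Protocol 5.7.1.2 allows, moves that sample to 408 h.

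**2. Reproduce the protocol's simulation figures (Table 2, section 1.10.2).** AUC over 12 weeks = Cavg × 2016 h gives 60.5, 88.7 and 104.8, against 61, 89 and 107 stated. I then fitted a linear bi-exponential model (1.5 h infusion, assumed) to the nine Cmax, Cmin and Cavg values. It matches all nine within 1.4%, with coefficients of 11.67 and 13.37 µg/mL per mg/kg and half-lives of 22.6 h and 6.9 days (165.8 h).

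Check on the terminal value, using accumulation index = 1 / (1 − 2^(−τ/t½)):

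| t½ | τ = 672 h (stated 1.06) | τ = 168 h (stated 1.97) |
|---|---|---|
| 6.9 d | 1.06 | 1.98 |
| 5 d | 1.02 | 1.61 |

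**3. Is 24 h post-distribution in that model?** Treating the dose as a bolus:

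- C(24) = 11.67 × 2^(−24/22.6) + 13.37 × 2^(−24/165.8) = 5.59 + 12.09 = 17.68
- C(168) = 0.07 + 6.62 = 6.69

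The fast phase is still 5.59 / 17.68 = 32% of the 24 h concentration. The two-point half-life is ln 2 × 144 / ln(17.68 / 6.69) = 103 h = 4.3 days.

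**4. Half-life returned by each sampling scheme.** Log-linear fit, t½ = ln 2 / (−slope), true value 6.9 days; Day 1 means the Cycle 1 single-dose profile:

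| Profile | Samples used | t½ (d) | Shortfall |
|---|---|---|---|
| B, Day 1 | 24, 168 h | 4.3 | 38% |
| B, Day 1 | 4, 24, 168 h | 4.0 | 43% |
| B, Day 15 | 24, 168 h | 5.0 | 27% |
| B, Day 15 | 4, 24, 168 h | 4.7 | 32% |
| A | 24–336 h | 5.6 | 19% |
| A | 48–336 h | 6.0 | 13% |
| A | 96–336 h | 6.5 | 5% |
| B, Day 15 with pre-dose sample | 24, 168, 336 h | 5.9 | 15% |

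About 44% of the Day 1 area lies beyond 168 h. Extrapolating it with the short slope understates AUC-infinity by 16–19% and overstates CL by 20–23%.

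**5. Sensitivity to an assumed model.** The documents give no human distribution half-life, so I took a 5-day terminal half-life, 30–50% of the initial concentration in the fast phase, and a fast half-life of 8–20 h. Over that whole grid:

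- Day 1: 3.1–4.2 d with the 4 h point, 3.4–4.7 d without it.
- Day 15: 3.5–4.4 d with it, 3.7–4.8 d without it.
- Day 15 with 24, 168 and 336 h: 4.3–4.9 d.
- Schedule A, 48–336 h: 4.5–5.0 d.

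**6. When the bias vanishes or reverses.** If decline is mono-exponential from 24 h on, two points return exactly 5.0 days. Protocol 1.10 reports clearance falling as dose rises, so I also tried saturable clearance (assumed Km 1–10 µg/mL, low-concentration clearance 1.1 mL/h/kg). At 2.0 mg/kg after Day 15, the 24 + 168 h estimate runs from 6% shorter (6.0 against 6.4 d) to 32% longer (3.1 against 2.4 d) than the 168–336 h half-life.

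**7. Is the 336 h sample measurable?** In the Table 2 model it is about 11 µg/mL at 2 mg/kg. The assay limit in PK plan 1.3.4 is 75 ng/mL.

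**The case against.** Several stronger readings are tempting, and the documents do not support them.

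- **A certain short bias.** Two points that are truly post-distribution give an imprecise slope, not a biased one. The bias needs distribution to be still running at 24 h. The Table 2 model supports that, and Protocol 1.4.2.2 reports a distribution phase of about 24 h in monkeys, but no human figure is given.
- **Forced use of the 4 h sample.** The plan sets no three-point minimum. An analyst could fit two points or report no half-life.
- **One direction at every dose.** The 5-day half-life is stated for 2.0 mg/kg and above. Planned Schedule B levels include 1.1 and 1.8 mg/kg, where none is given and the direction could reverse.
- **Pre-dose samples excluded by name.** They are not. The restriction to Cycles 1 and 3 only implies it.
- **A false comparison of schedules.** Neither document plans an A-versus-B test of half-life. PK is descriptive by cycle and dose level, and Schedule B was already closed. Schedule A is also somewhat short in the Table 2 model.

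The remedy is also partial. It cannot reach the Day 1 profile, because the Day 8 dose intervenes. Part of the fallback already exists: AUC0–168 is in Protocol 11.2, and AUC to the last sample is in the PK plan's Table 1.

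All of this limits the size and certainty of the bias. It leaves the two-sample design, the missing slope rule and the unused later sample as they are.

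**Conclusion.** The point holds in limited form. Schedule B half-life, and the AUC-infinity, CL and Vss that depend on it, are poorly determined, because beyond 4 h each profiled dose has two samples spanning 1.2 half-lives at the stated 5 days (0.87 at 6.9 days). Under the linear model that reproduces Table 2 and both accumulation indices, the half-life is short by 38–43% after Day 1 and 27–32% after Day 15. It reads roughly 10–40% below what Schedule A sampling returns for identical kinetics (5.0 against 5.6 days at the least, 4.0 against 6.5 at the most).

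These sizes rest on linear bi-exponential decline and the fitted 22.6 h fast phase. They are not established facts about the drug. A reader who sets the two schedules' half-lives side by side might infer a schedule effect; the sampling alone could produce one. The consequence is confined to descriptive secondary PK results on a closed schedule, but following the plan as written gives a worse estimate than the collected samples allow.

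**What to change.** In PK plan 2.1.4:

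1. For Schedule B, estimate half-life from the Day 15 profile and include the next cycle's Day 1 pre-dose sample (Cycle 2 after Cycle 1, Cycle 4 after Cycle 3), at its actual time, as Protocol 11.2 already requires for PK parameters.
2. State a rule for accepting a terminal slope on both schedules: a minimum number of points and a minimum span in half-lives.
3. For the Schedule B Day 1 profile, report Cmax and AUC0–168, and flag or withhold half-life, AUC-infinity, CL and Vss.
4. State that Schedule A and B half-lives are not directly comparable.

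The cost is plan wording, since the samples are part of the existing schedule. There are two drawbacks. Patients who stop before the next cycle have no Schedule B half-life. A small short bias also remains if the 24 h point is kept: 5.9 against 6.9 days in the Table 2 model, or 4.3–4.9 against 5 days in the assumed one.

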1.2. IMGN853

Because of its tumor specific expression and capacity to internalize small and large molecule ligands, FOLR1 has emerged as a promising target for antibody maytansinoid conjugate (AMC) therapy. AMCs combine the specificity of monoclonal antibodies to tumor antigens with the extraordinary cytotoxicity of maytansine derivatives, which are potent anti-microtubule agents that target proliferating cells. IMGN853 is an AMC designed to target FOLR1. It consists of the humanized anti-FOLR1 monoclonal antibody M9346A attached via a cleavable disulfide linker to the cytotoxic maytansinoid, DM4 (Figure 1).

ImmunoGen, Inc. Confidential Page 28 of 138

Figure 1: IMGN853 Structure

DM4 is \sim 2% by weight relative to Mab

Due to the nature of the conjugation process, the number of DM4 molecules attached to the monoclonal antibody ranges from 1 to 7 molecules per antibody, with an average of 3 or 4 DM4 molecules per antibody. Conjugation of the maytansinoid to the tumor targeting antibody ensures that the cytotoxic component remains inactive in the circulation. Release of the cytotoxic payload requires binding, internalization, and degradation of the antibody. The released payload then kills the cell by inducing G2-M arrest and cell death. Cellular processing of maytansinoid conjugates can also generate lipophilic catabolites that cross cell membranes and kill neighboring cells (Erickson 2006).

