1.4.3.2. Single-Dose IV Toxicity Studies with DM4 in Mice and Monkeys

Single dose toxicity studies were performed in mice and monkeys to assess the toxicity of DM4, the cytotoxic payload of IMGN853 and to compare its toxicity with the parent maytansinoid molecule, maytansine, and the closely related chemical analogue, DM1.

In the mouse study, a single dose of DM4 (1.2-4.1 mg/kg), DM1 (1.0-3.5 mg/kg), maytansine (1.2-3.2 mg/kg) or vehicle was administered intravenously and the mice were assessed clinically daily for 15 days. Necropsy was performed at day 15 or earlier for severe morbidity. The LD50 was about 2.2 mg/kg (6.6 mg/m2) for DM4 and DM1 and 1.8 mg/kg (5.4 mg/m2) for maytansine. DM1 and DM4 showed a similar toxicity profile at all 4 tested doses. All mice survived the 1.0 mg/kg DM1 dose and only 1/8 mice died in the group treated with 1.2 mg/kg DM4, a DM4 dose equivalent to the amount of DM4 present in a ~59 mg/kg dose of IMGN853. Drug-related changes were observed in the gastrointestinal tract and bone marrow in mice terminated early due to morbidity. The incidence and severity of the tissue lesions generally increased with increasing dose. The gastrointestinal lesions were characterized by mucosal attenuation, glandular cell loss, and necrosis. Bone marrow depletion roughly paralleled the incidence of changes in the alimentary tract, and was characterized by loss of cellularity across all myeloid components. The observed changes in the alimentary tract and bone marrow were generally resolved by 15 days post-administration in the surviving animals. No compoundrelated histopathologic abnormalities were observed in the liver, heart, lung, or kidney at any dose level of maytansinoid tested.

In the cynomolgus monkey study, DM4 was administered at 0.1 mg/kg via intravenous infusion. Animals were assessed clinically daily and necropsies were performed on Days 5 or 29.

ImmunoGen, Inc. Confidential Page 33 of 138

There were no clear DM4-related effects noted on physical examination, body temperature, electrocardiogram, indirect blood pressure, heart rate, urinalysis, or organ weight assessments.

DM4-related clinical pathology alterations included mild leucopenia primarily due to neutropenia, which corresponded microscopically to bone marrow depletion. Transient elevations in alkaline phosphatase values were noted in DM4-treated animals. Decreases in red blood cells and increases in platelets were seen in both control and treated animals.

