11.2. Pharmacokinetic Analyses

PK parameters (C_{max} , T_{max} , Terminal half-life ($t_{1/2}$), volume of distribution at steady state (Vss), clearance (Cl), AUC₀₋₂₄, AUC₀₋₁₆₈, AUC_{inf}) will be derived from plasma concentrations of IMGN853, total M9346A antibody and DM4 using the actual sampling times. Concentration data and all PK parameters will be listed per patient and summarized descriptively per dose. Standard algorithms of the non-compartmental pharmacokinetic analysis program, WinNonlin software, will be used for these analyses.

Individual plasma concentration vs. actual time profiles for each patient and treatment, as well as the mean (+/- STD) plasma concentration vs. scheduled time profiles for each dose level, will be presented graphically.

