1.3.4. Bioanalysis of PK Samples

The following table summarizes the bioanalytical methodology used to quantitate IMGN853, total antibody, and free payload (DM4 and s-methyl DM4).

Analyte	Method	Lower Limit of Quantitation	CRO Validation Report Number
IMGN853	ELISA	75.0 ng/mL	REYB2, REGD2
Total Antibody	ELISA	500 ng/mL	REYN2, REGE2
DM4, S-methyl-DM4	LC-MS	0.100 ng/mL	REGC2

ELISA, enzyme linked immunosorbent assay; LC-MS, liquid chromatography-mass spectrometry.

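### CL and Vss are planned for free DM4 and S-methyl-DM4, but these are released from the conjugate in an unknown amount, so neither parameter can be identified for them

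*SAP*

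**What the plan says.** The PK analysis plan (in the SAP document, with its own numbering) sets the rule in section 2.1.4. It names four analytes: "individual and mean concentrations for IMGN853, total antibody (TAb), DM4, and s-methyl-DM4 will be plotted vs. time by dose level". The next sentence carries the calculation: the parameters in Table 1 "will be calculated from these data via standard non-compartmental methods". Table 1 contains CL and Vss and makes no exception by analyte. It defines CL as the "volume of plasma that is completely cleared of the drug per unit time". The same paragraph asks for accumulation to be assessed for each analyte.

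Protocol 11.2 is explicit for DM4. Its parameter list includes Vss and Cl, and it says that the parameters "will be derived from plasma concentrations of IMGN853, total M9346A antibody and DM4 using the actual sampling times". S-methyl-DM4 is not named there, so for that species the commitment rests on the PK plan alone.

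On where the two small molecules come from, Protocol 1.2 says "Release of the cytotoxic payload requires binding, internalization, and degradation of the antibody", and PK plan 1.3.4 classes both as free payload. Neither document states which dose would enter a clearance calculation for them, gives a fraction released, or calls the result apparent.

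**The concern.** Non-compartmental CL is dose divided by AUC, and Vss is CL multiplied by mean residence time (MRT). Both need the amount of the analyte itself that enters the circulation, and the MRT must reflect that analyte's own disposition. For IMGN853 both conditions hold, because it is what is infused. For free DM4 and S-methyl-DM4 neither does. The input is an unmeasured release from the conjugate, spread over the conjugate's lifetime in plasma.

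Followed as written, the report would contain a DM4 clearance and a DM4 volume of distribution summarised under PK plan 2.1.3 with means, CVs and 95% confidence intervals. That gives an appearance of precision to numbers that do not estimate what their labels say. The optional look at CYP3A inhibitors and inducers in PK plan 2.1.6 is where misreading is most likely. If catabolite CL were used there, a change in elimination could not be told from a change in the fraction released.

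**Working it through.** **Inputs**
- DM4 content of the conjugate: Protocol Figure 1 (section 1.2) gives about "2% by weight relative to Mab".
- Dose equivalence: Protocol 1.4.3.2 describes 1.2 mg/kg as "a DM4 dose equivalent to the amount of DM4 present in a ~59 mg/kg dose of IMGN853". Protocol 1.4.3.3 equates 1.4–1.6 mg/kg DM4 with about 72–91 mg/kg by antibody weight.
- Conjugate half-life in patients (Protocol 1.10): about 5 days (120 h) at 2.0 mg/kg and above, about 1.5 days (36 h) at low doses.
- Free maytansinoid: Protocol 1.4.2.3 gives a half-life of about 2 h for maytansine in mice. No human value for DM4 is given.
- f, the fraction of payload that appears in plasma as the measured species: not in the documents. Values from 0.01 to 1 are an assumption, used to show the range.

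**Step 1: reproduce the stated content.** 1.2/59 = 2.03%; 1.4/72 = 1.94%; 1.6/91 = 1.76%. All agree with about 2%. Inverted, 59/1.2 = 49.2 mg of conjugate per mg of DM4 (up to 91/1.6 = 56.9).

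**Step 2: CL.** If the payload dose is Dp and true catabolite clearance is CLm, then AUC = f × Dp / CLm. Dividing a chosen dose D by this AUC gives CLm × D / (f × Dp). The error factor is therefore D / (f × Dp):

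| f | D = IMGN853 dose in mg (49.2/f) | D = payload-equivalent dose (1/f) |
|---|---|---|
| 1 | 49 | 1 |
| 0.5 | 98 | 2 |
| 0.1 | 492 | 10 |
| 0.01 | 4,917 | 100 |

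The result ranges from no error to several thousand-fold, depending on two quantities that the plan does not specify. The factors do not depend on the dose level given.

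**Step 3: Vss.** In a simple model (bolus conjugate, one compartment each, first-order release and elimination), observed catabolite MRT is the sum of the conjugate's and the catabolite's own mean residence times: (120 + 2)/ln 2 = 176 h. The catabolite's own MRT is 2/ln 2 = 2.9 h. The ratio is 1 + 120/2 = 61. With the low-dose conjugate half-life it is 1 + 36/2 = 19. The Vss error is the CL error times this ratio. At f = 1 with a payload-equivalent dose, where CL carries no error, Vss is still about 61-fold too high under these inputs.

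**Step 4: what is untouched.** IMGN853 is the dosed species, so its CL and Vss stand. Total antibody is nearly unaffected, since DM4 is only about 2% by weight. Catabolite Cmax, Tmax and AUClast need no dose term and stand as planned.

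**The case against.** The strongest reply is that this is a gap in labelling. The secondary objective (Protocol 2.3, and PK plan 1.2) is the PK of IMGN853. The endpoint list names Cl and Vss without an analyte, and Table 1 speaks of clearance of the drug. An experienced PK analyst might use a payload-equivalent dose, or leave CL and Vss out for catabolites. Payload exposure is judged on Cmax and AUC, which are sound. The MTD is defined by DLT counts (Protocol 4.1.3.3), and no rule in either document uses DM4 CL or Vss. In a comparison between groups, a constant dose-basis factor would cancel.

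Much of this stands, and it limits the consequences. It does not remove the point, because Protocol 11.2 names DM4 and the PK plan applies Table 1 to all four analytes. This is a stated rule that yields values without the meaning their labels carry. Nor would a change in f between groups cancel.

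A reader might infer more than the documents support:
- **That DM4 CL is bound to be wrong by orders of magnitude.** This needs the conjugate dose as numerator, or a small f. The plan states neither.
- **That Vss is about 3,000-fold too high (49.2 × 61 = 3,001).** This stacks the conjugate-dose assumption on a mouse half-life for a related molecule. Monkey data on DM4 in Protocol 1.4.2.3 also show loss within hours, which supports the direction but supplies no human figure.
- **That the secondary PK endpoint fails.** The IMGN853 values are unaffected.
- **That the catabolite terminal half-life is an error.** The observed slope is a valid description. It would mislead only if read as DM4's own elimination, and no human DM4 profile is given to show which process governs it.

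**Conclusion.** True CL and Vss of free DM4 and S-methyl-DM4 cannot be identified from this study's data as planned, yet the PK plan calculates them for both species and Protocol 11.2 does so for DM4.

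The CL error is 49/f-fold if the administered IMGN853 mg dose is used, and 1/f-fold if a payload-equivalent dose is used. In the latter case there is no error at f = 1. Vss is inflated as well, because residence time would be expected to reflect the conjugate's half-life of about 5 days. The documents cannot fix that amount for humans. The figure of about 60-fold holds at f = 1 with a payload-equivalent dose and an assumed free-payload half-life of about 2 h from mice.

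This should be corrected, but its reach is limited to two parameters for each of two catabolites.

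**What to change.** In PK plan 2.1.4 and Table 1, and in Protocol 11.2, either restrict CL and Vss to IMGN853 and total antibody, or report them for DM4 and S-methyl-DM4 only as apparent values with the dose basis stated. In either case, label the half-life of DM4 and S-methyl-DM4 as apparent. Keep their Cmax, Tmax and AUClast as planned.

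The cost is a few words in each place. No new samples or assays are needed. The downside is that two parameters per catabolite are dropped or relabelled.
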